One week after study enrollment, the pharmacy to which the prescription was called will be contacted to determine any prescriptions for asthma medications that were filled. Delivery of a doser CT device, which is used to assess medication adherence, will occur approximately one week after study enrollment. This device will be coupled with the ICS MDI (if one was obtained from the pharmacy) or with an albuterol MDI (if no ICS was filled). Families will be called two weeks after the ED visit to determine if there are any issues with device use. To ensure proper communication, a checking-in mailer will be sent out two weeks post-enrollment. This mailer will serve as a reminder to contact staff if participants encounter any issues with the doser CT device or if their contact information has changed. A home visit will be scheduled at one month to arrange for retrieval of the doser CT device. An "Unable to Contact Mailer" will be sent out to participants if staff are unable to contact them after several attempts.

**Routine Asthma Care Arm Protocol:** Participants in the routine asthma care arm will follow the treatment plan developed by the treating clinicians as part of routine care. The study nurses will provide the same asthma discharge instructions (see attached instructions), except for those instructions specific to ICS use.

One week after study enrollment, the child's pharmacy will be contacted to determine any prescriptions for asthma medications that were filled. Delivery of a doser CT device, which is used to assess medication adherence, will occur approximately one week after study enrollment. Unlike in the ICS Prescription Arm, the doser CT device for children in the control arm will be used with their albuterol MDI. Although this data will not be used for analysis, it makes the control arm intervention similar to the intervention arm from the perspective of the study participants. Families will be called after two weeks to determine if there are any issues with device use. To ensure proper communication, a checking-in mailer will be sent out two weeks post-enrollment. This mailer will serve as a reminder to contact staff if participants encounter any issues with the doser CT device or if their contact information has changed. A home visit will be scheduled at one month to arrange for retrieval of the doser CT device. An "Unable to Contact Mailer" will be sent out to participants if staff are unable to contact them after several attempts.

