( $p_1=0.35$ ) compared to the routine asthma care arm ( $p_0=0.6$ ), with 80% power to detect a statistically significant difference at an alpha of 0.05. Assuming 20% of participants will not be reached for follow up, and who will not have outcome data available when electronic medical records are audited, we will recruit 143 participants to achieve our sample size of 114.

**Data Safety and Monitoring Plan (DSMP):** The goals of the DSMP are three-fold. First, it is to ensure that there is no statistical difference in adverse events between the two study arms. Second, all serious adverse events will be reviewed by the members to provide direction on study continuation. Serious adverse events are considered very unlikely with this study protocol, since the two treatment conditions are both commonly utilized treatments in clinical practice. The third goal is to ensure that the intervention arm is not performing significantly better than the routine asthma care arm, as if this was identified early in the study, it would be unethical to withhold the intervention from the control arm.

Prior to beginning enrollment, we will have a conference call at which time the DSMP will be reviewed by the study PI and 2 Emergency Medicine attendings not affiliated with the study. The first DSMP data review will occur 6 months after the first participant has their 6 month data collection. Therefore this meeting will likely occur 12 months after study enrollment begins. Reviews will occur every 6 months thereafter.

The following outcome data will be provided to the DSMB along with the randomization assignments:

- Unscheduled medical visits to primary doctor's office for asthma
- ED visits for asthma
- Hospitalization for asthma
- Oral steroid courses for asthma
- Quality-of-life scores from the ITG-CASF
- Adverse events reported by parents at 6 month follow-up phone call
- Adverse events reported by study personnel
- Serious adverse events reported by study personnel\*

\* Any serious adverse events will be reported within 24 hours of occurrence to the IRB and DSMB. Study enrollment will be suspended until the DSMB and IRB have reviewed the event and made recommendations to the study PI.

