## Appendix A. Interviews at Home Visits

**Overview:** In addition to the RCT, we are adding a series of interviews of participants to help design the educational component that ED clinicians will provide to families at the time of ICS prescription to promote adherence. These interviews will occur during the second home visit of the original protocol during which the Doser CT devices, used to measure medication adherence will be queried.

**Recruitment:** Parents of children that were part of the ICS prescription arm in the RCT will be eligible for these interviews. Interviews will involve a convenience sample of these participants, occurring only when researchers trained in interviewing techniques are performing the home visit. Interviews will be recorded using two electronic recording devices (extra device to protect against primary device failure). Verbal consent will be used as the transcripts of the interviews will not include identifying information, and therefore a written consent would be the only link identifying the participant in this portion of the protocol.

Participants will be classified in one of three groups:

Group 1 (Did not fill ICS prescription) – Based on pharmacy calls outlined in the original protocol, we will determine which participants did not fill the ICS prescription by one week after enrollment.

Group 2 (Filled prescription, but non-adherent with appropriate ICS administration) – At the home visit, the Doser CT devices will be queried. Adherence will be defined as  $\geq 4$  days in the most recent 4 weeks of data with 4 doses of medication administered. If participants do not meet these criteria, they will be classified as non-adherent and included in Interview Group 2.

Group 3 (Filled prescription, and adherent with appropriate ICS administration) – Unlike group 2, participants will be in this group if they meet the adherence criteria outlined above.

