**Interview Protocol:** Using convergent interviewing techniques, we will perform a series of interviews with these three participant groups. Convergent interviewing uses a single open ended question, and allows the research participant to respond in an open-ended fashion for as long as possible. Probes are developed in response to these open-ended responses. After interim analysis of interviews, subsequent interviews may involve more focused probes. Because of this open-ended interviewing style, an interview guide is not used. The open-ended question that will be posed to early participants will be tailored to the 3 groups as follows:

Group 1 – “One of the ways to treat your child’s asthma is with inhaled steroids. At your recent emergency department visit, this was one of the recommendations made by the person that discharged you from the emergency department. What did you think of this recommendation?”

Groups 2 and 3 – “After your child’s recent visit to the emergency department, you filled a prescription for an inhaled steroid. Tell me what you think about using that medicine.”

Participants will be aware they are being recorded, and will be informed that all identifying information will be removed from transcripts that will be made from the recordings. Interviews will last approximately 30-45 minutes. Participants will be compensated \$20 for their time in completing the interview. These will be mailed as a check to the participant.

Interviews will be continued until the point where data saturation is reached which is defined by Attwater et al. as when two consecutive interviews occur in which no new themes are generated.

**Data analysis:** Based on the techniques outlined for convergent interviewing by Attwater, et al. the following steps will be employed:

1. The interviewer will analyze the data by coding the transcript passages into content codes using NVivo (version 8) a software program used to facilitate qualitative data analysis. The coding style will involve content analysis with codes in a tree node format.
2. A second researcher will code the same transcript independently.

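### Staff-reported adverse events are compared by arm, but only ICS-arm parents can have an open-ended interview about the medicine, so mild complaints can be ascertained more fully in that arm

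*Combined protocol and SAP*

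**What the plan says.** The first DSMP goal reads: "First, it is to ensure that there is no statistical difference in adverse events between the two study arms". The data supplied to the board with the randomization assignments include two non-serious adverse-event items. One is parent report at the 6-month call. The other is "Adverse events reported by study personnel". The second has no definition, no collection schedule and no scripted question.

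Appendix A adds interviews to the trial. On eligibility: "Parents of children that were part of the ICS prescription arm in the RCT will be eligible for these interviews". On timing: "These interviews will occur during the second home visit of the original protocol", which is the device-retrieval visit at one month. On who is reached: "Interviews will involve a convenience sample of these participants, occurring only when researchers trained in interviewing techniques are performing the home visit". Parents who filled the prescription hear a prompt that includes "you filled a prescription for an inhaled steroid. Tell me what you think about using that medicine". Parents who did not fill it are asked about the recommendation instead. Interviews last 30-45 minutes and use probes. Under the appendix's data analysis steps, recurring content leads to new probes in later interviews, meant to find out how common it is.

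Control families also have the one-month visit: "A home visit will be scheduled at one month to arrange for retrieval of the doser CT device" appears in both arm protocols. The summary table gives both arms the two-week call and the calls at one, two and four months. No interview or comparable open question is described for controls.

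**The concern.** A between-arm comparison of adverse events is fair only if events have the same chance of being noticed in each arm. Here one arm can have a long, open conversation about the study medicine with a member of study staff who knows the arm, and the other cannot. A parent may mention a mild or short-lived complaint at month 1 that would not come up at a brief device-retrieval visit or be recalled at month 6. If the interviewer reports it, it joins the staff-reported count for the ICS arm only. Because early interviews shape later probes, a complaint raised by one family may then be asked about in others, all of them in the ICS arm. At stake is the board's reading of safety: it could see an excess under ICS when the true rates are equal.

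**Working it through.** The plan states no figure on this point, so there is none to reproduce. The check has two parts.

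**1. Contacts side by side**

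| Contact | ICS arm | Control arm |
|---|---|---|
| One-week visit (device delivery) | yes | yes |
| Two-week call | yes | yes |
| One-month visit (device retrieval) | yes | yes |
| Open-ended interview at that visit | convenience sample | none |
| Calls at one, two and four months | yes | yes |
| Blinded 6-month call | yes | yes |

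Only the interview lacks a match. Of these contacts, only the 6-month call is stated to be made by a blinded researcher.

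**2. Possible size**

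The documents give neither the number of interviews nor a capture rate, so these are assumed:
- f = share of ICS-arm parents interviewed: 0.25 or 0.50. With 143/2, or about 71 per arm, that is about 18 or 36 interviews.
- r = chance that a mild event is captured at the common contacts: 0.5, 0.7 or 0.8.
- True event rates are equal in the two arms.

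*Upper case: the interview captures every event in an interviewed family.* The captured fraction is r in the control arm and r + f(1−r) in the ICS arm. Hence
- apparent ratio = 1 + f(1−r)/r
- share of captured ICS-arm events found only by interview = f(1−r) / [r + f(1−r)]

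*Even-spread case.* A month-1 interview cannot reveal events in months 2 to 6. If events are spread evenly over six months, the gain f(1−r) becomes f(1−r)/6.

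| f | r | Ratio, upper | Interview-only share, upper | Ratio, even spread | Interview-only share, even spread |
|---|---|---|---|---|---|
| 0.25 | 0.5 | 1.25 | 20.0% | 1.04 | 4.0% |
| 0.25 | 0.7 | 1.11 | 9.7% | 1.02 | 1.8% |
| 0.25 | 0.8 | 1.06 | 5.9% | 1.01 | 1.0% |
| 0.50 | 0.5 | 1.50 | 33.3% | 1.08 | 7.7% |
| 0.50 | 0.7 | 1.21 | 17.6% | 1.04 | 3.4% |
| 0.50 | 0.8 | 1.125 | 11.1% | 1.02 | 2.0% |

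Worked line for f = 0.50, r = 0.5: upper ratio 1 + 0.25/0.5 = 1.50; even-spread ratio 1 + (0.25/6)/0.5 = 1.08.

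*Sensitivity to low background capture.* Take the staff-reported item alone and assume staff capture 25% of complaints without an interview and 75% with one. At f = 0.50 the ICS capture is 0.5 × 0.75 + 0.5 × 0.25 = 0.50, against 0.25 in controls, a ratio of 2.0. With 114/2 = 57 per arm and a 20% true rate, expected counts are 57 × 0.20 × 0.50 = 5.7 and 57 × 0.20 × 0.25 = 2.9. By exact enumeration of a two-sided 5% pooled chi-square test, with true rates of 20% to 30%, the chance of a false signal is 4.5-4.8% with no interviews, 8-10% at f = 0.25 and 17-24% at f = 0.50. This too lets the interview reach all six months of events. Under even spread the f = 0.50 ratio falls from 2.0 to 1 + 0.5 × (0.50/6)/0.25 = 1.17. The DSMP names no test for adverse events, so the chi-square is also an assumption.

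**The case against.** The strongest reply is that no text routes interview content into adverse-event reporting. The interviews exist to design an educational component, their analysis is qualitative coding, transcripts carry no identifiers and recordings are erased. This stands in part. A reader might infer that complaints voiced to interviewers do enter the by-arm data; the documents support only that they can. De-identification does not close the route, since the interviewer is study staff in the family's home, and every interviewee belongs to the ICS arm. Nothing excludes such reports either.

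A reader might also infer that control families have no contact at month 1, or that the board cannot separate sources at all. Neither is so. Both arms share the visit and the interim calls, and the DSMP already lists 6-month parent reports apart from staff reports. What is missing is a breakdown within the staff-reported item.

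The reach of the interviews is also limited: a convenience sample, stopped at saturation, in which parents who did not fill are not asked about using the medicine. This limits the size, not the direction. Finally, only ICS families are taught about possible side effects at discharge. That is a separate source of unequal reporting, and the change proposed here does not remove it.

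**Conclusion.** The point holds as a documented difference in opportunity to detect mild complaints, confined to the staff-reported item. If interview complaints are counted, the bias runs toward apparent harm under ICS. Its size cannot be determined from the documents. For r between 0.5 and 0.8 and a quarter to a half of ICS parents interviewed, the apparent ratio is at most 1.06 to 1.50, and about 1.01 to 1.08 with events spread evenly over six months. Front-loaded events or lower background capture would raise these figures; fewer interviews would lower them. It would be a mistake to read 1.06 to 1.50 as the expected excess, because that range needs a month-1 interview to reveal six months of events. Nor does the point extend to the 6-month parent reports or to the chi-square and t-test efficacy analyses. The change is worth making because it costs almost nothing, although confidence in the size of the effect is low.

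**What to change.** In the DSMP:
- Record, for each adverse event, the contact at which it was first reported.
- Base the between-arm comparison on events captured at contacts both arms receive: the 6-month call, the common calls and the home visits, excluding the interview.
- Give the board all events first raised in an Appendix A interview in a separate ICS-arm listing, and also show totals that include them, so that no safety information is lost.
- State that serious events remain reportable within 24 hours whatever the source, as now.

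The cost is one source field on the adverse-event form and a few lines in the DSMP, with no added visits or staff. The small downside is that some genuine mild ICS events will appear in the listing and totals rather than in the main comparison.

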## Appendix A. Interviews at Home Visits

**Overview:** In addition to the RCT, we are adding a series of interviews of participants to help design the educational component that ED clinicians will provide to families at the time of ICS prescription to promote adherence. These interviews will occur during the second home visit of the original protocol during which the Doser CT devices, used to measure medication adherence will be queried.

**Recruitment:** Parents of children that were part of the ICS prescription arm in the RCT will be eligible for these interviews. Interviews will involve a convenience sample of these participants, occurring only when researchers trained in interviewing techniques are performing the home visit. Interviews will be recorded using two electronic recording devices (extra device to protect against primary device failure). Verbal consent will be used as the transcripts of the interviews will not include identifying information, and therefore a written consent would be the only link identifying the participant in this portion of the protocol.

Participants will be classified in one of three groups:

Group 1 (Did not fill ICS prescription) – Based on pharmacy calls outlined in the original protocol, we will determine which participants did not fill the ICS prescription by one week after enrollment.

Group 2 (Filled prescription, but non-adherent with appropriate ICS administration) – At the home visit, the Doser CT devices will be queried. Adherence will be defined as  $\geq 4$  days in the most recent 4 weeks of data with 4 doses of medication administered. If participants do not meet these criteria, they will be classified as non-adherent and included in Interview Group 2.

Group 3 (Filled prescription, and adherent with appropriate ICS administration) – Unlike group 2, participants will be in this group if they meet the adherence criteria outlined above.

**Interview Protocol:** Using convergent interviewing techniques, we will perform a series of interviews with these three participant groups. Convergent interviewing uses a single open ended question, and allows the research participant to respond in an open-ended fashion for as long as possible. Probes are developed in response to these open-ended responses. After interim analysis of interviews, subsequent interviews may involve more focused probes. Because of this open-ended interviewing style, an interview guide is not used. The open-ended question that will be posed to early participants will be tailored to the 3 groups as follows:

Group 1 – “One of the ways to treat your child’s asthma is with inhaled steroids. At your recent emergency department visit, this was one of the recommendations made by the person that discharged you from the emergency department. What did you think of this recommendation?”

Groups 2 and 3 – “After your child’s recent visit to the emergency department, you filled a prescription for an inhaled steroid. Tell me what you think about using that medicine.”

Participants will be aware they are being recorded, and will be informed that all identifying information will be removed from transcripts that will be made from the recordings. Interviews will last approximately 30-45 minutes. Participants will be compensated \$20 for their time in completing the interview. These will be mailed as a check to the participant.

Interviews will be continued until the point where data saturation is reached which is defined by Attwater et al. as when two consecutive interviews occur in which no new themes are generated.

**Data analysis:** Based on the techniques outlined for convergent interviewing by Attwater, et al. the following steps will be employed:

1. The interviewer will analyze the data by coding the transcript passages into content codes using NVivo (version 8) a software program used to facilitate qualitative data analysis. The coding style will involve content analysis with codes in a tree node format.
2. A second researcher will code the same transcript independently.
  - a. Content codes will be developed *during the course* of the analysis as follows. As the first two transcripts are being analyzed content codes will be proposed by the two coders (one of whom is the PI). These content codes will be discussed and modified by consensus agreement of the two coders. If a given content code is agreed upon, it will be added to the coding scheme.
  - b. The coding scheme derived after the first two transcripts are analyzed will then be used for the next two transcripts.
    - i. If new content codes are identified by individual coders during coding of the second transcript, these will again be discussed and modified by consensus agreement and added to the coding scheme if agreed upon.
  - c. This process will continue with analysis occurring after every two interviews.
3. After every two interviews within a participant group, the interviewers will again meet to compare codes assigned to each transcript. At these meeting, themes developed from the content will also be discussed and agreed upon themes recorded.
4. For each theme generated, previous content will be reviewed to look for disagreement and agreement.
  - a. When agreement with previous content is identified, probes will be developed for use in subsequent interviews to test the validity of this apparent agreement by looking for disconfirming views, and identify how widely this phenomenon occurs.

- b. When disagreement with previous content is identified, probes will be developed for use in subsequent interviews to provide an explanation for this disagreement and identify how widely this phenomenon occurs.
5. This process of recycling will continue until two successive interview within a given interview group provide no new information.

**Protecting Confidentiality:** The content of the focus group discussions will be transcribed and de-identified by removing names and any other identifying information. When transcription is complete, digital recording files will be erased.

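### Appendix A gives a convenience sample of ICS-arm parents, and no control parents, a paid interview about the child's ICS at month 1, with about five months of outcome collection still to run

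*Combined protocol and SAP*

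**What the plan says.** **The interviews (Appendix A).** Eligibility under Recruitment is by randomized arm: "Parents of children that were part of the ICS prescription arm in the RCT will be eligible for these interviews". Not every such parent is interviewed: "Interviews will involve a convenience sample of these participants", and only when a trained interviewer is making the visit. On timing, the Overview states: "These interviews will occur during the second home visit of the original protocol". The ICS Prescription Arm Protocol fixes that visit: "A home visit will be scheduled at one month to arrange for retrieval of the doser CT device". Under Interview Protocol, "Interviews will last approximately 30-45 minutes", and parents receive $20 "for their time in completing the interview". No number is set: "Interviews will be continued until the point where data saturation is reached", and the Data analysis steps apply that rule within each of three groups. Group 1 (prescription not filled by one week) hears that inhaled steroids are a way to treat the child's asthma and were recommended at the ED visit, and is asked for its view. Groups 2 and 3 (filled) are asked about using the medicine.

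**Matching of contact (main protocol).** Control children use a Doser on their albuterol inhaler. Its data are not analyzed. The Routine Asthma Care Arm Protocol gives the reason: "it makes the control arm intervention similar to the intervention arm from the perspective of the study participants". The summary table schedules home visits, the mailer and the retention calls for both arms. It lists no interview.

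**Outcomes and analysis.** Health care use is counted over six months from enrollment, leaving out only the first week, and quality of life is taken at the six-month call. The Data Analysis Plan is intention-to-treat with a chi-square test and a t-test. It does not mention interviewed families.

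**The concern.** After discharge and the called-in prescription, the interview is the only scheduled contact that differs between the arms by design. It concerns the treatment under test and comes while most of the outcome window is still open. A long conversation about inhaled steroids could lead a non-filler to fill the prescription, or a filler to use it more regularly. The extra $20 raises a family's scheduled payments from $40 ($10 + $10 + $20) to $60, which could affect retention. Parents are not blinded, so their quality-of-life answers could also move.

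Any such effect enters the ICS arm alone and is counted as an effect of ED prescribing. The analysis could not separate it afterwards, because no record of interview status is planned. Appendix A chooses verbal consent precisely to avoid a document that identifies the interviewee.

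**Working it through.** The plan gives no figure for the interviews, so there is nothing to reproduce. The check has three steps.

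**1. Timing.** The interview is at about month 1 and outcomes run to month 6, so 6 − 1 = 5 months of health care use, and the whole six-month quality-of-life score, come after it. Doser adherence is read at the same visit and is largely untouched.

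**2. Shift in the arm difference.**

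Inputs from the documents:
- 143 recruited at 1:1, so 143/2 = 71.5, or about 72 in the ICS arm.
- 114 evaluable, so 57 per arm.
- Planned event proportions of 0.60 (control) and 0.35 (ICS), a difference of 25 points.

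Assumptions (not in the documents):
- k = 12, 20 or 30 families interviewed.
- e = 0, 5, 10 or 20 points' reduction in six-month event risk among those interviewed.
- Interviewed families are lost to follow-up at the same rate as the rest of the arm.

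Formula: shift = (k/72) × e.

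| Interviewed | Share of arm | e = 0 | e = 5 | e = 10 | e = 20 |
|---|---|---|---|---|---|
| 12 | 16.7% | 0 | 0.8 | 1.7 | 3.3 |
| 20 | 27.8% | 0 | 1.4 | 2.8 | 5.6 |
| 30 | 41.7% | 0 | 2.1 | 4.2 | 8.3 |

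As a share of the planned 25 points, the e = 10 column is 7%, 11% and 17%, and the largest cell is 8.3/25 = 33%. If the interview discouraged use, the signs would reverse.

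**3. Chance of a false finding for ICS.** Suppose everything in the ICS package other than the interview does nothing. The ICS-arm proportion is then p₁ = 0.60 − shift against p₀ = 0.60, with n = 57 per arm. For a two-sided 5% test,

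P(significant, favoring ICS) = Φ[(shift − 1.96 × SE₀)/SE₁],

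where p̄ = (p₁ + p₀)/2, SE₀ = √[p̄(1 − p̄) × 2/57] and SE₁ = √[(p₁(1 − p₁) + p₀(1 − p₀))/57].

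For k = 30 and e = 10: p₁ = 0.558, SE₀ = 0.0925, SE₁ = 0.0924, so Φ[(0.0417 − 0.1813)/0.0924] = Φ(−1.51) = 6.5%.

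At e = 10 the probability is about 3.8%, 4.9% and 6.5% for 12, 20 and 30 interviews, against 2.5% with no interview effect.

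**The case against.** Several points against the concern are sound.

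- **Reach.** Only a convenience sample is interviewed, and interviewing stops at saturation. A reader might infer that the whole ICS arm receives the interview; Appendix A does not say so, and any effect is diluted accordingly.
- **Attribution.** A reader might also infer that the interview is what prevents the trial from isolating prescription alone. The documents do not support that. The ICS Prescription Arm Protocol already adds ICS-specific nurse teaching to the prescription, so the contrast was always a package. The interview adds a partial layer, and one that Appendix A presents as additional to the trial.
- **Direction.** The interview elicits views and does not teach. It opens with one question, has no guide, and its probes look for disconfirming views. It could bring out doubts as well as prompt use, and Group 3 is already adherent by the appendix's definition. A benefit to the ICS arm is plausible, most clearly for Group 1, who hear the recommendation restated, but nothing in the documents shows it.
- **Reporting and retention.** The six-month caller is blinded. Office visits are checked with the child's doctor and steroid courses with the pharmacy. The Power Analysis refers to auditing electronic records for children not reached, and both arms have retention calls and fallback home visits. Reporting bias is therefore a concern mainly for quality of life.
- **Ceiling on the effect.** A child with a counted event before the interview cannot have that event removed, so a large effect on the yes/no outcome is harder to reach.

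These points limit the size of the problem and leave its direction open. They do not remove it: the contact is one-sided, avoidable, unrecorded, and at odds with the protocol's own reason for the sham Doser.

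**Conclusion.** The point holds as a partial, one-arm co-intervention. The timing, the ICS-only eligibility and the absence of a control counterpart are all on the page.

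The size cannot be known from the documents. Under the stated assumptions the shift runs from 0 to about 8 points against the planned 25. The upper end needs both 30 interviews and a 20-point effect, which is 80% of the effect planned for the whole intervention (20/25). A modest shift is more likely unless a large share of the arm is interviewed. This does not invalidate the trial; it is an avoidable weakness that a change of timing removes.

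**What to change.** **Timing.** Amend Appendix A so that each interview takes place only after that family's six-month outcome data are complete. Hold it by telephone or as a separate contact. The interviewer should not be the blinded outcome researcher, and the interview should not be combined with the fallback home visit for outcomes: only ICS-arm families are eligible, so either arrangement could reveal the arm. Groups can still be assigned from the week-1 pharmacy check and the month-1 Doser data.

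**Interviews held at month 1.** Log interview status by study ID, kept apart from the de-identified transcripts. This is feasible, since the team must already know whom to send the $20 check. Report the number interviewed, and describe the contrast as prescription plus ED teaching plus interviews in a subset.

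**Sensitivity analysis.** Keep all randomized children in their arms, raise the event risk of interviewed ICS-arm children by 5, 10 and 20 points in turn, and recompute the difference and the test. Label it supportive. Dropping the interviewed children instead would break the randomized comparison.

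**Cost.** Parents will recall the first month less well, the opening questions (worded for a recent visit) will need adapting, and interviewed families have one separate contact. The number of interviews and the payment do not change.
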